10.2.6. Adverse Events

Adverse events will be mapped to a Medical Dictionary for Regulatory Activities (MedDRA)

Study code: 052/SI Hyalistil Bio PF Mono

version 19.1 preferred term and system organ classification.

If a patient has multiple adverse events within the same system organ class in the treatment period, the subject will only be counted once at the system organ class level in adverse event frequency tables. Should an event have a missing severity or relationship, it will be classified as having the highest severity and/or strongest relationship to study medication. Summaries of incidence rates (frequencies and percentages) of individual AEs by MedDRA system organ class and preferred term will be prepared. Such summaries will be displayed for all TEAEs, TEAEs by maximum severity, and TEAEs by strongest relationship to clinical investigation medical device.

Serious AEs and AEs leading to discontinuation of investigational product will also be summarized.

All adverse events reported will be listed for individual patients showing both verbatim and preferred terms.

Any adverse event with a missing onset date will be considered to be a TEAE occurring during the treatment period.

10.2.7. Premature Discontinuation

Dropout patients will be defined as patients who prematurely discontinued the study. Patients who had stopped the study treatment but were still being followed in the study were not considered as dropouts.

All data available until the premature discontinuation will be taken into account.

10.3 Multicenter Studies Considerations

Not applicable.

10.4 Multiple Comparisons and Multiplicity

When necessary, the multiplicity-adjusted p -value will be calculated by multiplying the unadjusted p -value by the number of times compared.

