4. CLINICAL INVESTIGATION DESIGN

This clinical investigation is a multicentric prospective observational open-label, non-interventional clinical investigation evaluation, during the conventional clinical practice, the performance and safety of the daily instillation of Hyalistil Bio PF device in the treatment of patients affected by eye *discomfort* in particular in case of ocular dryness.

The clinical evaluation period was run approximately for 4 months from first patient first visit (FPFV) March 14th, 2023, to last patient last visit (LPLV) August 3rd, 2023. All patients were followed from enrolment until study end date, which was occur when, in compliance with the normal clinical practice, the last patient was undergo the Study Termination Visit (35± 4 days from the first instillation of study product).

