10. STATISTICAL METHODS

Descriptive analysis will be performed by using absolute rate, percentage and frequency tables for qualitative variables.

Normally distributed continuous data will be reported as minimum, maximum, mean and standard deviation, whereas non- normally distributed data as medians and IQR.

Categorical variables will be analyzed by using Yates-corrected chi-square test or Fisher's exact test when appropriate. The McNemar's test will be used to analyze paired nominal data. Differences in endpoints between baseline and different timepoints will be assessed using paired t-test for normally distributed data, whereas the Wilcoxon signed-rank test will be used for non-normally distributed data.

Data distribution will be evaluated through the Kolmogorov-Smirnov test.

A p-value <0.05 will be considered statistically significant.

Analysis will be performed using SAS version 9.4 for Windows (SAS Institute Inc., Cary, NC, USA).

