15. LIST AND SAMPLES OF TABLES, FIGURES AND GRAPHS

The following lists of tables might not be exhaustive. Additional tables can be produced if necessary.

For each comparison of the various quantitative endpoints (visit 2 versus visit 1 and visit 3 versus visit 1) the descriptive statistics of the endpoint at the two visits will first be calculated and then the P-value will be calculated to assess the statistical significance of the difference. This difference will also be reported as a percentage from baseline.

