5 PERFORMANCE DATA (SECONDARY ENDPOINTS)

-NEI Scale ITT population

Table 5.1.1 TOTAL SCORE NEI ITT population (v1) vs (v3)

Table 5.2.1 TOTAL SCORE NEI ITT population (v1) vs (v2)

Table 5.3.1 TOTAL SCORE CORNEA ITT population (v1) vs (v3)

Table 5.3.2 TOTAL SCORE CORNEA ITT population (v1) vs (v2)

Table 5.4.1 TOTAL SCORE CONJUNCTIVA ITT population (v1) vs (v3)

Table 5.4.2 TOTAL SCORE CONJUNCTIVA ITT population (v1) vs (v2)

-TFBUT ITT POPULATION

Table 5.5.1 TFBUT ITT population (v1) vs (v2)

-Questionnaire SANDE ITT population

Table 5.6.1 TOTAL SCORE SANDE ITT population (v1) vs (v3)

Table 5.7.1 TOTAL SCORE SANDE ITT population (v1) vs (v2)

Study code: 052/SI Hyalistil Bio PF Mono

Table 5.8.1 SEVERITY DRYNESS/IRRITATION ITT population (v1) vs (v3)

Table 5.8.2 SEVERITY DRYNESS/IRRITATION ITT population (v1) vs (v2)

Table 5.9.1 FREQUENCY DRYNESS/IRRITATION ITT population (v1) vs (v3)

Table 5.9.2 FREQUENCY DRYNESS/IRRITATION ITT population (v1) vs (v2)

-Questionnaire VAS ITT population

Table 5.10.1 Question "I feel satisfied using this treatment? ", ITT population

Table 5.10.2 Question "With this treatment, I have a feeling of freshness?", ITT population.

Table 5.10.3 Question "With this treatment, I have a feeling of relief?", ITT

Table 5.10.4 Question "This treatment contributed to reduce my pain due to eye dryness?", ITT population

Table 5.10.5 Question "This treatment is comfortable? ", ITT population

Table 5.10.6 Total score VAS, ITT population

-DEQS ITT POPULATION

Table 5.11.1.1 DEQS Summary score ITT population (v1) vs (v3)

Table 5.11.2.1 DEQS Bothersome Ocular Symptoms subscale ITT population (v1) vs (v3)

Table 5.11.3.1 DEQS Impact on Daily Life subscale ITT population (v1) vs (v3)

Table 5.11.4.1 DEQS-GES ITT population (v1) vs (v3)

-IGAS

Table 5.12.1 IGAS ITT populations

-IOP ITT POPULATION

Table 5.13.1 IOP ITT population (v1) vs (v3)

Table 5.14.1 IOP ITT population (v1) vs (v2)

Study code: 052/SI Hyalistil Bio PF Mono

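### SAP 10.4 leaves adjustment of 19 secondary tests to discretion, with no stated family, and uses plain multiplication where Holm's method gives the same error control with more power

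*SAP*

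**What the plan says.** SAP 10.4 consists of one sentence: "When necessary, the multiplicity-adjusted p -value will be calculated by multiplying the unadjusted p -value by the number of times compared". SAP 10 sets one threshold for every test: "A p-value <0.05 will be considered statistically significant".

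SAP 15 plans p-values at both follow-up visits: "For each comparison of the various quantitative endpoints (visit 2 versus visit 1 and visit 3 versus visit 1) the descriptive statistics" are calculated first, then a p-value for the difference. The secondary tables in SAP 15.2 start with "Table 5.1.1 TOTAL SCORE NEI ITT population (v1) vs (v3" and run through staining, TFBUT, SANDE, DEQS and IOP. SAP 13.2 adds tests of best corrected visual acuity (BCVA) that have no listed table. The mock tables have no field for an adjusted p-value. Neither document sets a testing order or labels the secondary tests exploratory.

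The study is open-label (SAP 4.3). SAP 4 gives its end as "to last patient last visit (LPLV) August 3rd, 2023"; SAP 1.1 dates version 1 of the SAP October 10th, 2023.

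**The concern.** Two analysts could both follow this SAP and report different lists of significant secondary results. One might adjust nothing. Another might multiply by two for the two visits, or by the full number of tests. The choice is left to a time when an open-label study has already completed its last visit. Secondary statements on staining, symptoms, quality of life and acuity would then carry no defined error rate.

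There is also a free improvement. When the rule is used, plain multiplication gives up power that Holm's method keeps at the same family error.

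**Working it through.** **Plan's own figure.** SAP 7 gives a mean change of 1.56 and SD 1.91, so the standardised effect is 1.56/1.91 = 0.817. At two-sided alpha 0.01 and power 0.80, a paired t-test needs 21 patients. A Wilcoxon test needs 22 (relative efficiency 3/π) or 25 (minimum efficiency 0.864). The stated 23 is consistent with these. The documents state no family error rate.

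**Count of secondary performance tests (SAP 13.2 and 15.2).**

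| Endpoint | Tests |
|---|---|
| NEI total, cornea, conjunctiva, each at Visits 2 and 3 | 6 |
| TFBUT, Visit 2 against Visit 1 | 1 |
| SANDE total, severity, frequency, each at Visits 2 and 3 | 6 |
| DEQS summary, two subscales, general eye status (GES) | 4 |
| *Subtotal in listed tables* | *17* |
| BCVA at Visits 2 and 3 (text of 13.2 only) | 2 |
| **Total** | **19** |

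Testing TFBUT at Visit 3 against Visit 2, a secondary objective in SAP 3.2 with no listed table, would make 20. Adding the two IOP safety tests to the 19 makes 21.

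**Timing.** August 3 to October 10, 2023 is 28 + 30 + 10 = 68 days.

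**Family error with no adjustment, all nulls true.**
- Independent tests: 1 − 0.95^19 = 62.3% (58.2% for 17 tests, 65.9% for 21).
- Simulated with 19 equally correlated normal test statistics, correlation assumed: 52% at 0.3, 41% at 0.5, 28% at 0.7 and 15% at 0.9.
- Bound under any dependence: 19 × 0.05 = 95%.

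**If the multiplier is read as two per endpoint.** Seven endpoints have two visits, giving 14 tests at 0.025. The other five stay at 0.05. Under independence, 1 − 0.975^14 × 0.95^5 = 1 − 0.702 × 0.774 = 45.7%.

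**Multiplication against Holm over the same 19 tests.** Multiplying by 19 means a per-test level of 0.05/19 = 0.0026. Simulated paired t-tests with n = 23 and effect 0.817 assumed for each real effect gave this average power:

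| Real effects | Correlation | Multiplication | Holm |
|---|---|---|---|
| 19 of 19 | 0 | 69.5% | 89.5% |
| 19 of 19 | 0.5 | 69.6% | 84.7% |
| 10 of 19 | 0 | 69.4% | 75.0% |
| 10 of 19 | 0.5 | 69.2% | 74.3% |

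Holm rejects everything that multiplication rejects, and sometimes more, and it also controls the family error under any dependence.

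**The case against.** This is a 28-patient, single-arm, observational post-market study. Neither document calls the secondary results confirmatory, and the analyses lead with summaries. Multiplication is a valid method, so choosing it is not an error. Read beside SAP 15, the multiplier may well be meant as two per endpoint. On this view a line of clarification is enough.

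Much of this stands. A sponsor may decide that secondary tests need no control, but the plan must then say that they are descriptive. This SAP instead declares significance at 0.05 and promises adjustment without saying when. The two-per-endpoint reading is plausible but unstated, and would still leave no control across endpoints.

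Four stronger inferences are not supported:
- *That the false-claim risk is 62%.* The NEI total is the sum of its parts, the SANDE total is computed from its two items, and the DEQS total pools its subscales, all in the same patients. Independence cannot hold. Nor is 62% a mathematical maximum.
- *That Holm accounts for any gain from a shorter list.* Holm's strictest step over five tests equals multiplication by five. At n = 28 and effect 0.817, power is 83% at 0.05/19 and 93% at 0.05/5 = 0.01; that gap comes from family size alone.
- *That corneal and conjunctival scores are new in the SAP.* Protocol 19 lists both under the staining endpoint; only their separate tests are new. The DEQS subscale analyses are new, and GES does not appear in the protocol.
- *That the tests were chosen after seeing results.* The dates do not show this. SAP 6.2 places the final analysis after database lock.

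**Conclusion.** The gap is real and confined to secondary claims. SAP 10.4 does not determine which results will be called significant. With no adjustment and all nulls true, the chance of at least one false claim among the 19 tests is about 15% to 52% over assumed correlations of 0.9 to 0.3. The documents give no correlations, so this is a range and not an estimate.

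The method itself can be improved at no cost in error control. The gain in average power from Holm is about 15 to 20 points if all 19 effects are real, and about 5 to 6 points if 10 are. Both figures borrow the TFBUT planning effect, because no secondary effect sizes are given. The primary comparison of Visit 3 with Visit 1 is a single test and is unaffected, provided it is not multiplied; SAP 10.4 should say so.

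**What to change.** Rewrite SAP 10.4 before database lock:

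1. State that the single primary TFBUT test (Visit 3 against Visit 1) is not multiplied.
2. Replace multiplication with Holm's step-down method at two-sided 0.05 over a fixed family of protocol-stated secondary comparisons:
   - NEI total at Visits 2 and 3;
   - secondary TFBUT, first settling whether this is Visit 3 against Visit 2 (Protocol 11, SAP 3.2) or change from baseline (Protocol 23, SAP 13.2);
   - BCVA at Visits 2 and 3;
   - SANDE at Visits 2 and 3, first stating whether the endpoint is severity and frequency (Protocol 19) or the combined score whose formula appears only in SAP 13.2;
   - DEQS total at Visit 3.
3. Report p-values for the separate corneal and conjunctival scores, DEQS subscales, GES and IOP as descriptive, with no significance claim.

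With one secondary TFBUT test, the family has 2 + 1 + 2 + 2 + 1 = 8 tests using the combined SANDE score, or 10 using its two components. Visit 2 must stay in, because the protocol states staining, acuity and SANDE objectives at that visit.

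The cost is SAP text, an adjusted p-value column and a few table rows: BCVA, and TFBUT Visit 3 against Visit 2 if kept. The sponsor gives up significance claims for the tests added in the SAP and for IOP. No planned summary is lost.

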10.5 Data Safety Monitoring Board (DSMB)

Not applicable.

11 STUDY PATIENTS

11.1 Disposition of Patients

Patient disposition will be presented in terms of the numbers and percentages of patients who completed the study and discontinued from the study patients who are not discontinued from the study will be considered study completers. The disposition of the patients will be described in the

CONSORT figure.

The number and percentage of patients prematurely discontinued from the study and the reasons for study discontinuation will be for all enrolled patients. The reasons for study discontinuation that will be summarized include: AE, protocol violation, administrative reasons (e.g., inability to continue, lost to follow up), Sponsor termination of study, patient choice, and other. A patient listing will be provided that includes the date of and reason for premature study discontinuation.

11.2 Protocol Deviations

Protocol deviations will be registered in the monitoring visits reports, performed during the study. Protocol deviations will be described in Table and in Listing.

The number and percentage of patients with any, major, and minor protocol deviations will be summarized for all enrolled patients. Major protocol deviations are defined as protocol deviations that may impact primary performance endpoint; other protocol deviations are classified as minor. Protocol deviations will be assessed prior to database lock and unmasking. The number and percentage of patients with any protocol deviation will also be summarized for the following categories: Informed Consent, Inclusion / Exclusion, Instillation of investigational product. Improper Protocol Procedures at Site, Site's Failure to Report Serious Adverse Event (SAE) / AE, Visit Out of Window, patient's Use of Prohibited Concomitant Medication, and Other. A patient listing will be provided that includes the date, description of each deviation and the classification of whether the deviation was judged to be major or minor.

The Sponsor will consider the following criteria for exclusion of a patient from the PPS:

- Impossibility to assess the compliance with investigational medical product application (patients who have not returned the amount of used single dose containers and/or empty/unused medical device boxes);
- Missing primary performance data;
- Failure to satisfy any inclusion/exclusion criteria;
- Intake of prohibited medications.

12 PERFORMANCE ANALYSIS

12.1 Analysis datasets

See Section 10.

12.2 Demographics and Baseline Characteristics

Demographic (age, gender, ethnic origin) and baseline characteristics (vital signs, weight, height, medical history, and physical examination) will be summarized by using minimum, maximum, mean, standard deviation or median and IQR for continuous variables and number of patients and percentage per category for categorical variables.

12.3 Measurements of Treatment Compliance

Details by patients will be reported and compliance will be estimated as the percentage of administrations given with respect to the administrations planned.

$$\text{Compliance (\%)} = \frac{\text{Numbers of vial dispensed} - \text{Number of unused vials returned}}{\text{Number of doses planned}}$$

Compliance will be presented categorical as <50% 50-80% and >80%, were:

- 1) <50% = Poor Compliance
- 2) 50-80% = Moderate Compliance
- 3) >80% = Good Compliance

No further analyses will be planned on compliance. All other collected data including diary information on treatment compliance will be evaluated during the BDRM for relevant protocol deviations and will be listed.

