14.1 Description of product

Composition

Components	Amount (100 ml)
Sodium hyaluronate	g 0.200
Trometamol (TRIS)	g 0.242
Sodium chloride	g. 0.600
Hydrochloric acid q.s. to	pH 7.2
Potassium chloride	g 0.250
Purified water q.s. to	ml 100

Indications

Hyalistil Bio PF contains sodium hyaluronate, a natural polymer also presents in structures of the human eye, whose chemical physical characteristics gives the solution hydrating, muco-mimetic and viscoelastic properties.

Hyalistil Bio PF coats the eye surface, guaranteeing its adequate lubrication and reducing the friction caused eyelid movements. It also hydrates the ocular surface and assures protection during the healing processes of corneal epithelium.

Therefore, **Hyalistil Bio PF** combines lasting relief with maximum comfort Characteristics and mechanism of action

Presentation

30 single-dose containers of 0.25 ml

Dosage and administration

The patient will instill 1 drop of **Hyalistil Bio PF** in the conjunctival fornix, 4 times a day, in the affected eye.

Instructions for use

Wash / sanitize your hands. Before use make sure that the single-dose container is intact. Detach the single-dose from the strip. Open by turning the top without pulling. Instill avoiding that the tip of the container comes into contact with the eye or any other surface.

Study code: 052/SI Hyalistil Bio PF Mono

Contraindications

Hypersensitivity to one of the ingredients.

Warnings

There are no known interactions of the product with the administration of drugs for ophthalmic use. However, it is recommended not to administer other drugs or medical devices for ophthalmic use within 10 minutes after administration of **Hyalistil Bio PF**.

It is not necessary to remove contact lenses before administering **Hyalistil Bio PF** as the product does not alter the physical characteristics, including transparency, of the most common soft and rigid contact lenses.

The use of the product may occasionally cause intolerance (mild burning or irritation).

Undesirable effect

The use of the product may occasionally cause intolerance (mild burning or irritation).

Interactions with other drugs or medical device for ocular use:

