14.4 Name or number of the model/type to permit full identification

The name of the model to permit full identification of the medical devices is: **Hyalistil Bio PF**.

15. Investigational medical device storage and handling

The Sponsor will offer, like free samples, individual boxes containing an adequate supply of the investigational product to be instilled during the study to each subject.

The Pharmacist and/or Investigator will be responsible for receipt, proper storage, and usage of experimental product, as well as for the investigational product distribution, collection of used and unused vials and final disposal of the remaining investigational product.

The investigational product must be stored not exceeding 25 °C at the investigational sites, in an appropriate locked room accessible only to the pharmacist, the Investigator, or a duly designated person.

A temperature probe and data logger will accompany the investigational product on shipment. It is essential that the investigational sites verify the temperature excursion during shipment against acceptable storage conditions in order to identify potential stability concerns during shipment. These must be immediately communicated to the Sponsor that will decide upon appropriate actions to be taken. The investigational product will be stored in a locked place, sheltered from light.

PI, or a delegate, will maintain an inventory record of the investigational product received.

At the conclusion of the study, a final medical device accountability will be performed. If any supplies are missing, this will be indicated together with an explanation for the discrepancy.

During the Visit 1 the study personnel will give the patient boxes containing the investigational product.

Patient should bring the investigational product, boxes containing for 35±4 days of treatment, at home and store not exceeding 25 °C.

As previously described, each single-dose container must be used immediately after opening.

Do not touch the end of the open container and do not put it in direct contact with the eye.

Each single-dose container has the amount needed to treat both eyes.

Any residue must not be reused, as **Hyalistil Bio PF** does not contain preservatives and the remaining product could become contaminated, exposing to the risk of eye infections.

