Any deviations from the recommended storage conditions should be reported by Pharmacist and/or Investigator to the Sponsor, and the use of the investigational product should be suspended

Study code: 052/SI Hyalistil Bio PF Mono

until they have given authorization for its continued use. The investigational product supplies are to be used only in accordance with this clinical investigation plan.

Investigational Medical Devices Delivery Plan

Box delivery	Boxes to be provider
Visit 1 (0 days)	5 Boxes of 30 single dose containers

16. Investigational medical device accountability

The Pharmacist and/or Investigator will confirm the receipt of the investigational product supply in writing by signing and dating standard of investigational product accountability forms.

At the Study Termination Visit the patients will return the used or unused study boxes to the Investigator.

In case of premature study discontinuation, patients will undergo an Early Termination Visit (ETV). During the ETV the patients will return the amount of used single dose containers and empty/unused medical device boxes returned by patients to the centre. The Pharmacist and/or Investigator will keep a cumulative inventory and dispensing records and will maintain all supplies under adequate security.

An accurate product disposition record will be kept, specifying the date and amount dispensed to each patient.

Inventory record of receipt, use or loss of investigational product will be retained. This inventory record must be available for inspection by the Sponsor and regulatory inspection at any time. Copies of this record will be provided to the Sponsor by the CRO throughout the duration of the study.

Partially used or unused study investigational product boxes will be verified and returned by the Investigator/ Institution to the investigational product manufacturer, at the end of the study.

During the observational study, the Investigator will complete the "investigational product accountability forms". After completion of the clinical investigation, the unused study investigational product will be destroyed after authorization by the Sponsor by an authorized company according to GCP regulations.

17. Other allowed therapies

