- Evaluation of any reported adverse events/incidents**;
- Ocular examination of both eyes:
 - External Ocular Examination;
 - BCVA test through the ETDRS at 4 m distance;
 - Symptom Assessment in Dry Eye by SANDE questionnaire;
 - Evaluation of Intraocular pressure (IOP);
 - Tear film break-up time with fluorescein (TFBUT)[◊];
 - Ocular surface staining (NEI score) with fluorescein;

Patients were return to the clinical site on day 35 ± 4 days from the first instillation of medical device under investigation (Study Termination Visit).

Study Termination Visit (on the 35th day from the first instillation of medical device under investigation) (window ± 4 days)

The final visit is defined as the visit performed on 35 ± 4 days after the first instillation of medical device under investigation[○].

In case of premature study discontinuation, patients will undergo an Early Termination Visit (ETV):

The following procedures will be performed:

- Assessment of treatment compliance (reconciliation of the amount of used single dose containers and empty/unused medical device boxes returned by patients to the centre)[§];
- Current medical conditions;

- Concomitant medications;
- Evaluation of any reported adverse events/incidents**;
- Ocular examination of both eyes:
 - o External Ocular Examination;
 - o BCVA test through the ETDRS at 4 m distance;
 - o Symptom Assessment in Dry Eye by SANDE questionnaire;
 - o Evaluation of Intraocular pressure (IOP);
 - o Tear film break-up time with fluorescein (TFBUT)[◊];
 - o Ocular surface staining (NEI score) with fluorescein;
- Administration of the VAS scale on the degree of satisfaction to the treatment;
- DEQS questionnaire administration;
- Evaluation of the safety of the experimental product through the compilation of the IGAS scale;
- Restitution of remaining medical devices [§].

* Start of the treatment (window + 1 day).

** In case of adverse events/incidents all assessments considered necessary by the Investigator was performed, including the possible suspension of treatment.

*** Variable because it is based on the planned visit schedule according to clinical practice for the individual patient Visit 2 (windows of \pm 2 days).

° All patients enrolled were treated for 35 days. The Study Termination Visit is variable because it is based on the planned visit schedule according to clinical practice for the individual patient (window \pm 4 days).

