10.2.4 Treatment Compliance

Treatment duration per patient will be estimated as the number of days between the first and last treatment administration. Absolute rate and percentage of days of treatment will be reported.

Compliance will be estimated as the percentage of administrations given with respect to the administrations planned. Compliance will be also reported categorical as <50%, 50-80% and >80%. In particular:

1. <50% = Poor Compliance
2. 50-80% = Moderate Compliance
3. >80% = Good Compliance

Details by patients about compliance well be reported

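### SAP 12.3 counts every unused vial not returned as an instillation, and SAP 11.2 sets no low-compliance exclusion, so under-users can be classed as Good and stay in the per-protocol set

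*SAP*

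**What the plan says.** SAP 10.2.4 states the intention: "Compliance will be estimated as the percentage of administrations given with respect to the administrations planned". SAP 12.3 repeats it and gives the formula. The numerator is vials dispensed minus "Number of unused vials returned", and the denominator is "Number of doses planned", which is not defined further. Results are classed as Poor (<50%), Moderate (50-80%) or Good (>80%), with no upper limit.

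Used containers are also to be returned. SAP 4.1 lists "reconciliation of the amount of used single dose containers" at the Study Termination Visit, and SAP 5.3 describes the compliance evaluation as a count of containers and boxes. The formula does not use that count.

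SAP 11.2 gives four criteria for leaving the per-protocol (PP) set: compliance not assessable, missing primary data, failed eligibility and prohibited medication. The first reads "Impossibility to assess the compliance with investigational medical product application" and is explained as failure to return used containers and/or boxes. No compliance percentage is named. Mock Table 3.2, for the PP population, has a row for Poor compliance.

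Protocol section 23 analyses the primary endpoint on PP and repeats it on ITT. SAP 8.3 and 8.4 make ITT the performance population and PP supportive.

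**The concern.** The formula measures vials that did not come back, which is not the same as instillations given. Any unused vial left at home, lost or discarded raises the score, and the error from such vials runs in one direction only. The returned empties, which could show the gap, are left out of the calculation.

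Two things are at stake. Compliance is a listed evaluation parameter, and its classes could look better than actual use. PP membership also has no compliance rule except that compliance be assessable, so a patient with clear evidence of low use can remain in the set meant to represent treatment as planned. The sample size is 23, with 28 to be enrolled, so each patient is 1/28 = 3.6% to 1/23 = 4.3% of the analysis.

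**Working it through.** The documents give no compliance result to reproduce. The check applies the SAP 12.3 formula to the plan's own quantities.

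**Inputs**
- Dispensed: "5 Boxes of 30 single dose containers" (Protocol section 15, delivery plan), so 5 × 30 = 150 vials.
- Planned use: "in the conjunctival fornix, 4 times a day, in the affected eye" (Protocol 14.1), so 4 instillations a day.
- Vials per instillation: one. "Each single-dose container has the amount needed to treat both eyes" (Protocol section 15), and residue may not be reused.
- Duration: 35 ± 4 days (Protocol section 18), so 31 to 39 days.

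**Range of the formula.** Compliance = (150 − unused returned) / (4 × days).

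| Days | Planned doses | No unused vial returned | All 150 returned unused | Leftover if fully adherent |
|---|---|---|---|---|
| 31 | 124 | 150/124 = 121.0% | 0% | 26 |
| 35 | 140 | 150/140 = 107.1% | 0% | 10 |
| 39 | 156 | 150/156 = 96.2% | 0% | −6 |

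The 121.0% requires planned doses to be counted over 31 days. If they are fixed at 140, the ceiling is 107.1%. The −6 shows that the supply and the longest permitted duration do not match; those passages must be reconciled.

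**An under-user with partial returns (35 days, 140 planned).** The return counts are illustrative. The patient uses 60 vials and brings back the 60 empties.
- Use shown by the empties: 60/140 = 42.9%, Poor.
- 30 of the 90 unused vials returned: (150 − 30)/140 = 85.7%, Good. Unaccounted vials: 150 − 60 − 30 = 60.
- 40 of the 90 returned: (150 − 40)/140 = 78.6%, Moderate.

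**How many vials must go missing.** Good requires more than 0.8 × 140 = 112 vials counted as used. A complete non-user reaches it only if at least 113 of 150 unused vials do not come back. A half-user (70 vials) needs more than 112 − 70 = 42 of 80 unused vials unreturned.

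**Why the obvious replacements fail**
- *Used containers alone:* a patient who took all 140 doses but kept only 60 empties scores 60/140 = 42.9%, Poor.
- *Denominator of 4 × days from first to last administration* (the duration in SAP 10.2.4): a patient who stops after 15 days and 60 doses scores 60/(4 × 15) = 100%, against 60/140 = 42.9%.
- *A cap at 100%:* this hides unaccounted vials and over-use.

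**The case against.** A reader might infer that non-users are reported as compliant and kept in PP. The rules do not produce that in general. A non-user who returns the vials scores 0% and is Poor, and one who returns nothing meets the first exclusion in SAP 11.2. Only partial returners are at issue.

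There are further safeguards. SAP 12.3 sends other compliance data, including diary information, to the BDRM. Protocol section 15 requires missing supplies to be explained. Instillation of the product is a deviation category, and a deviation that may affect the primary endpoint is major and leads out of PP. Protocol section 22 withdraws non-compliant subjects. Compliance is descriptive only, values above 100% change no class, and Table 3.2 would show any patient classed as Poor who is kept in PP.

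Much of this stands, and it limits the point to partial returners. It does not close the gap. None of these rules has a numerical threshold. It is unclear whether the not-assessable criterion covers someone who returned some of both kinds of container. No diary appears in the visit procedures or the SAP 9.1 variable list. Table 3.2 would show the example patient as Good.

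A reader might also infer that the primary result is biased in the product's favour. The documents do not show this: if the product works, keeping under-users in a before-after comparison would tend to dilute the change.

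**Conclusion.** The point holds for patients who return part of their supply. The formula does not measure what SAP 10.2.4 says it measures, can exceed 100% (107.1% at 35 days; 121.0% if planned doses are counted over 31 days), and can move a patient from Poor to Good (42.9% to 85.7%). PP has no compliance threshold, so such patients, and even those correctly classed as Poor, stay in PP unless a major-deviation ruling or a withdrawal removes them.

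This rests on one vial per instillation, four instillations a day and 150 vials dispensed, all taken from the protocol. The number of patients affected cannot be estimated, because no return or loss rate is given. The consequence is an unreliable compliance table and an undefined PP boundary; an inflated primary result is not demonstrated. A change is worth making because it is cheap and the protocol tests the primary endpoint on PP.

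**What to change.** Amend the SAP wording before database lock:

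1. **SAP 12.3, two figures.** Report used containers returned / planned doses as a lower bound, and (dispensed − unused returned) / planned doses as an upper bound. List unaccounted vials per patient. Flag values above 100% instead of capping them.
2. **SAP 12.3, denominator.** Define planned doses as the planned daily instillations times the days from first instillation to the Study Termination Visit or, after early discontinuation, over the planned treatment period. Do not stop the count at the last administration.
3. **SAP 11.2.** Add the SAP's own <50% class to the PP exclusions, applied when the upper bound is below 50%. Send patients whose two figures fall in different classes to the data review before lock. The example patient (42.9% and 85.7%) would be reviewed, not removed automatically.

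The cost is wording and a listing. PP may lose a few patients. The lower bound understates use when empties are discarded, and it cannot be computed if the used-container count was not recorded. SAP 9.1 lists compliance fields without showing what they hold, and the SAP (10 October 2023) postdates the last visit (3 August 2023), so this must be checked first.
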